Study design		Using a traditional "3+3" dose-escalation design, subjects will be sequentially assigned to one of three dose groups (2.8×10^{10} units, 1.4×10^{11} units, and 7.0×10^{11} units per dose, once daily, with continuous intranasal instillation for 4 days). Each dose group will include 3 subjects, who will be enrolled one by one. The exploration of the next dose can only proceed if no dose-limiting toxicity (DLT) is observed in the 3 subjects. If 1 out of the 3 subjects experiences DLT, an additional 3 subjects will be enrolled in the same dose group; the exploration of the next dose can only move forward if no DLT is observed in these newly added 3 subjects. A minimum of 6 and a maximum of 18 subjects will be recruited during the dose exploration phase. Patients will receive other standard medical treatments in accordance with the recommendations in the 2022 Chinese Guidelines for Secondary Prevention of Ischemic Stroke and Transient Ischemic Attack , including antiplatelet drugs or anticoagulants, antihypertensive drugs, lipid-lowering drugs, and glucose-lowering drugs.
Outcome Measures	Primary Outcome Measure	Dose-Limiting Toxicity (DLT) Related to hUC-MSC-sEV-001 Includes: (1) Grade 3-4 severe adverse events occurring on day 14 (+-2), graded according to Common Terminology Criteria for Adverse Events (CTCAE) V5.0; (2) NIHSS score increase of ≥ 4 from baseline on day 14 (+-2); NIHSS score assessed by a professional rehabilitation physician;(3) Symptomatic intracranial hemorrhage occurring on day 14 (+-2); detected via CT scan and patient symptom presentation.
	Secondary Outcome Measures:	Serious adverse events related to the investigational drug within 90 (+-7) days. Distribution of Modified Rankin Scale (mRS) Scores within 90 (+-7) days. Barthel Index within 90 (± 7) days. Five-level, five-dimensional EuroQol (EQ-5D-5L) . Proportion of Modified Rankin Scale (mRS) Scores of 0-2 within 90 (+-7) days. All-cause mortality at 90 (+-7) days. Changes in infarct volume at 14 (+-2) days compared to baseline. Change from Baseline in National Institutes of Health Stroke Scale (NIHSS) Score.
Follow-up duration		Baseline (0~1 day), 7 (± 1) days, 14 (± 2) days, 90 (± 7) days
Sample size		6-18 subjects need to be included.

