Single-center, prospective, dose-escalation clinical trial.

(2) Trial Administration Strategy

A traditional "3+3" dose-escalation design will be adopted. Subjects will be sequentially assigned to one of three dose groups (2×10^{10} units, 1×10^{11} units, 5×10^{11} units per administration, once daily for 4 consecutive days via intranasal instillation). Each dose group initially enrolls 3 subjects, with sequential enrollment (i.e., the next subject is enrolled only after the previous subject completes the 14-day DLT observation period).

- If no DLT is observed in 3 subjects of a dose group, the study proceeds to the next higher dose level.

- If 1 out of 3 subjects experiences DLT, an additional 3 subjects are enrolled in the same dose group. If no DLT is observed in the additional 3 subjects, the study proceeds to the next higher dose level; if ≥ 1 additional subject experiences DLT, the current dose level is defined as the maximum tolerated dose (MTD), and dose escalation is terminated.
- A total of 6 to 18 subjects will be recruited during the dose-escalation phase.

(3) Study Suspension or Early Termination

The study will be suspended or terminated early if any of the following occurs:

- Violation of the *Good Clinical Practice (GCP)* or the *Administrative Measures for Stem Cell Clinical Research (Trial)*;
- Emergence of new safety or efficacy data on MSC-sEVs indicating that the trial poses a serious risk to patient safety or is clearly ineffective;
- Failure to enroll subjects as scheduled for 3 consecutive months;
- Major protocol deviations that affect the validity of study data;
- Request for termination by the sponsor or regulatory authorities.

2. Subject Selection Criteria

(1) Inclusion Criteria

- Confirmed diagnosis of acute ischemic stroke (in accordance with the *Chinese Guidelines for the Diagnosis and Treatment of Acute Ischemic Stroke (2023)*);
- Aged 18-70 years, regardless of gender;
- Anterior circulation occlusion (internal carotid artery, middle cerebral artery M1/M2 segment) confirmed by CTA or MRA;
- mRS score of 0-1 before the current stroke episode (indicating no or minimal disability prior to the index event);
- ASPECTS ≥ 6 on non-contrast computed tomography (NCCT) or diffusion-weighted imaging (DWI) after stroke onset (indicating a small to moderate infarct volume);
- NIHSS score ≥ 6 at screening (indicating moderate to severe neurological deficit);

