1. Neurological Function Scales:

- **NIHSS:** Assesses the severity of neurological deficits (range: 0-42; higher scores indicate more severe deficits). Administered at baseline, Day 7, Day 14, and Day 90.
- **mRS:** Assesses functional independence (range: 0-6; scores 0-2 indicate good functional outcome). Administered at baseline, Day 7, Day 14, and Day 90.
- **Modified Barthel Index (MBI):** Assesses activities of daily living (range: 0-100; higher scores indicate better independence). Administered at baseline, Day 14, and Day 90.
- **EQ-5D-5L:** Assesses health-related quality of life (including mobility, self-care, usual activities, pain/discomfort, anxiety/depression; scored as a utility value ranging from -0.291 to 1.0). Administered at baseline, Day 14, and Day 90.

2. Cerebral Perfusion Parameters (CTP):

- Measured at baseline, Day 14, and Day 90: cerebral blood volume (CBV), cerebral blood flow (CBF), mean transit time (MTT), time to peak (TTP) in the infarct core and penumbra.
- Changes in perfusion parameters from baseline are used to evaluate the improvement of cerebral blood flow.

3. Infarct Volume Measurement:

- Infarct volume is measured on DWI using the ABC/2 method (A: maximum length, B: maximum width perpendicular to A, C: number of slices × slice thickness).
- Changes in infarct volume from baseline to Day 14 are used to evaluate infarct progression or regression.

5. Outcome Evaluation Indicators

(1) Primary Safety Endpoints

- **Dose-Limiting Toxicity (DLT):** Assessed within 14 days of the first dose, defined as any of the following:
 1. Grade 3-4 AE related to the study drug (CTCAE V5.0), such as severe nasal bleeding, anaphylactic reaction, or hepatic injury;
 2. Increase in NIHSS score ≥ 4 points from baseline (indicating significant neurological deterioration);
 3. Symptomatic intracranial hemorrhage (confirmed by CT/MRI and associated with neurological deterioration).

(2) Secondary Safety Endpoints

1. **SAE Incidence:** Proportion of subjects with drug-related SAEs within 90 days of the first dose;
2. **All-Cause Mortality:** Proportion of subjects who die from any cause within 90 days of the first dose;
3. **Laboratory Abnormality Rate:** Proportion of subjects with Grade ≥ 3 laboratory abnormalities (e.g., thrombocytopenia, elevated liver enzymes) within 90 days.

(3) Efficacy Endpoints

1. **Functional Outcome:** Proportion of subjects with mRS score 0-2 at Day 90;

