2. **Neurological Improvement:** Mean change in NIHSS score from baseline to Day 14 and Day 90; proportion of subjects with NIHSS score reduction ≥ 4 points at Day 14;
3. **Functional Independence:** Mean change in MBI score from baseline to Day 90; proportion of subjects with MBI score ≥ 60 (indicating moderate independence) at Day 90;
4. **Quality of Life:** Mean change in EQ-5D-5L utility value from baseline to Day 90.

(4) Exploratory Endpoints

1. **Infarct Volume Change:** Mean change in infarct volume from baseline to Day 14;
2. **Cerebral Perfusion Improvement:** Mean changes in CBF, CBV, MTT, and TTP from baseline to Day 14;
3. **Correlation Analysis:** Correlation between baseline characteristics (e.g., age, NIHSS score) and efficacy outcomes.

6. Study Protocol Flow and Evaluation Indicators

First Visit [Baseline (Day 0)]

1. **Informed Consent:** The investigator explains the study protocol to the subject/legal representative, who signs the informed consent form if willing to participate.
2. **Screening Assessments:**
 - Demographic and clinical data collection;
 - Vital signs measurement;
 - Laboratory tests: CBC, clinical chemistry, coagulation function, serum electrolytes, infectious disease screening, tumor markers, urinalysis, pregnancy test (if applicable);
 - Imaging examinations: NCCT, DWI, MRA/CTA, chest X-ray, 12-lead ECG;
 - Neurological scales: NIHSS, mRS, MBI, EQ-5D-5L.
3. **Eligibility Confirmation:** The investigator reviews the inclusion/exclusion criteria and confirms eligibility.
4. **Study Drug Administration:**
 - Nasal mucosa pretreatment with hyaluronidase (150 U per nostril);
 - Instill the first dose of hUC-MSC-sEV-001;
 - Measure vital signs 30 minutes after administration.
5. **Documentation:** Record combined medications, rehabilitation therapy plans, and any AEs.

Second Visit (Day 7 ± 1)

1. **Safety Assessments:**
 - Vital signs measurement;
 - Laboratory tests: CBC, clinical chemistry, urinalysis;
 - AE monitoring and recording.
2. **Efficacy Assessments:**
 - Neurological scales: NIHSS, mRS.
3. **Documentation:** Record combined medications and rehabilitation therapy progress.

Third Visit (Day 14 ± 2)

1. Safety Assessments:

- Vital signs measurement;
- Laboratory tests: CBC, clinical chemistry, coagulation function, serum electrolytes, infectious disease screening, tumor markers, urinalysis;
- Imaging examinations: 12-lead ECG, DWI, FLAIR, CTA/CTP;
- AE monitoring and recording (including SAE follow-up).

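### The 14-day DLT period, the Day 14 ± 2 visit that measures it and the release of the next subject do not match, and the synopsis and Section 5(1) classify a Day 15–16 NIHSS rise differently

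*Protocol*

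**What the plan says.** Four places in the Protocol bear on this.

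- **Release of the next subject, Section 1(2):** "the next subject is enrolled only after the previous subject completes the 14-day DLT observation period". The condition is a period of time. No completed visit, NIHSS score or recorded DLT status is named.
- **Escalation:** Section 1(2) says "If no DLT is observed in 3 subjects of a dose group, the study proceeds to the next higher dose level". The synopsis says "The exploration of the next dose can only proceed if no dose-limiting toxicity (DLT) is observed in the 3 subjects" and adds only that subjects enter one by one; it states no 14-day wait.
- **DLT window:** Section 5(1) has "Assessed within 14 days of the first dose, defined as any of the following", with no tolerance. Its second criterion is "Increase in NIHSS score ≥ 4 points from baseline (indicating significant neurological deterioration)". The synopsis, under the primary outcome measure, has "NIHSS score increase of ≥ 4 from baseline on day 14 (+-2)" and "Symptomatic intracranial hemorrhage occurring on day 14 (+-2)", and puts the same ± 2 days on Grade 3–4 events.
- **When NIHSS is taken:** Section 4(3) schedules it at baseline, Day 7, Day 14 and Day 90. Section 6 gives the windows: Day 7 ± 1, and "Third Visit (Day 14 ± 2)" for the visit in question.

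**The concern.** One-by-one entry exists so that each subject's DLT status is known before the next is exposed. Here the clock that releases the next subject and the visit that settles DLT status run on different windows, and the document defines the DLT window in two ways.

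Two things are at stake. First, a site following the wording could dose the next subject on Day 15 while the previous subject's Day 14 visit is booked, within its window, for Day 16. If the previous subject is the last of a cohort, the next one receives a dose five times higher (Section 1(2): 2×10^10, 1×10^11, 5×10^11; the synopsis figures differ but have the same ratio). Second, the primary outcome of a subject seen on Day 15 or 16 can depend on which page is applied. A 3+3 design has no slack for that, because each decision turns on one event.

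**Working it through.** The check is day arithmetic. No sample-size, power or alpha figure is involved, so there is none to reproduce.

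**Inputs**
- Day 0 is enrolment and first dose (Section 3(2), Section 6).
- The DLT period is 14 days from first dose (Sections 1(2) and 5(1)), so it ends on Day 14.
- The Day 14 visit window is 14 ± 2 (Section 6).
- The preceding NIHSS window is 7 ± 1 (Section 6).

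**Visit days against the release point**
- Permitted days: 14 − 2 to 14 + 2 = 12, 13, 14, 15, 16.
- Days after the period ends: 15 and 16, that is 2 of 5.
- Longest gap from release to the scheduled NIHSS: 16 − 14 = 2 days.
- Last scheduled NIHSS in hand at Day 14 if the visit is on Day 15 or 16: from Day 6 to 8. Its age is 14 − 8 = 6 to 14 − 6 = 8 days.

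**An NIHSS rise of 4 or more, first found at the visit**

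| Visit day | Section 5(1) (to Day 14) | Synopsis (Day 14 ± 2) | NIHSS available when the 14-day period ends? |
|---|---|---|---|
| 12, 13, 14 | DLT | DLT | Yes |
| 15, 16 | Not a DLT | DLT | No |

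Neither definition closes the gap. With the synopsis window, a countable DLT can arise after the next subject has been released. With the Section 5(1) window, an on-schedule visit on Day 15 or 16 cannot yield a countable NIHSS DLT at all.

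**Effect of one such event on the 3+3 decision**
- First three subjects: counted, 1/3, and three more subjects enter at the same dose. Not counted, 0/3, and the study escalates.
- Expanded cohort with one earlier DLT: counted, 2/6, and escalation ends (Section 1(2)); two DLTs at one dose level also end the study under Sections 2(7) and 11(6). Not counted, 1/6, and the study escalates.

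**The case against.** The strongest reply is that an observation period is complete only when its observation has been made, and that escalating if no DLT is observed presupposes that DLT status is known. That is a sensible reading and may well be what the sponsor means. But the text names a 14-day period and no visit, and a site enrolling on Day 15 ahead of a Day 16 visit would not breach its wording. This reply also leaves the two DLT windows in conflict.

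Several stronger conclusions that a reader might draw are not supported:

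- **That a Day 15–16 worsening simply falls outside the DLT window.** This is so only under Section 5(1). The synopsis counts it. The defect is the conflict between the two.
- **That the subject is unobserved between the Day 7 and Day 14 visits.** Adverse events are recorded from consent to 30 days after the last dose (Sections 4(2) and 8(2)), that is to Day 3 + 30 = 33. Subjects are told to report new symptoms at once (Section 3(4)), and stroke deterioration after dosing leads to withdrawal (Section 2(4)). Section 5(1) does not confine its NIHSS criterion to scheduled visits, so an unscheduled score within 14 days would count. Its related Grade 3–4 event and symptomatic haemorrhage criteria do not depend on the visit date. What is missing at release is the scheduled score compared with baseline.
- **That a Day 12 or 13 visit is also a fault.** It leaves 1 or 2 days of the period without a later scheduled NIHSS until Day 90, but that is an ordinary feature of a symmetric visit window and contradicts nothing.
- **That 2 of 5 is a probability.** It counts permitted days. The Protocol does not say how often visits would fall on Day 15 or 16.

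**Conclusion.** The point holds as a mismatch among three things that must agree in a 3+3 design: the DLT window, the visit that measures it, and the release of the next subject. As written, a visit on either of the two latest permitted days comes up to 2 days after the next subject or dose level may start, and a qualifying NIHSS rise found there is a DLT in the synopsis and not in Section 5(1). This goes beyond missing detail, because following Section 5(1) and the visit schedule to the letter can leave out an event found at an on-schedule visit and turn 1/3 into 0/3.

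The conclusion rests on counting from Day 0 as first dose, which the Protocol states, and on reading the 14-day period as elapsed time, which is the plain wording but not the only possible reading. The exposure is limited to one scheduled assessment and at most 2 days. The documents give no basis for estimating how often it would change a decision. It should be corrected before enrolment because the DLT is the primary outcome and drives every escalation decision.

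**What to change.** Reconcile the synopsis and Sections 1(2), 5(1) and 6 on a single DLT window, and make that window agree with the window of the visit that measures it. Which window applies is for the sponsor to decide. In Section 1(2), tie release of the next subject and each escalation expressly to completion of that DLT assessment, with DLT status recorded.

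The cost is protocol wording and at most about 2 days between consecutive subjects. Eighteen subjects have 17 intervals, so the maximum added time is 17 × 2 = 34 days. For scale, 17 intervals of 16 days are 272 days; adding the latest Day 90 visit (90 + 7 = 97 days) gives 369 days, before any recruitment gaps, against a planned study of two years (November 2025 to November 2027).

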Furthermore, this research will greatly promote the translational application of MSC-sEVs in the treatment of other diseases, provide a scientific basis for the government to improve the treatment system for stem cells and their derivatives, enhance the level of patient care, reduce mortality and disability rates, and benefit a large number of patients—thereby generating substantial economic and social benefits. It will also accelerate the rapid development of MSC-sEV applications, align with the national strategy of promoting innovation-driven development, and play a positive role in safeguarding the growth of social and economic benefits.

Main Research Content

Based on adherence to the Good Clinical Practice (GCP) principles for national clinical trial research and the standardized procedures of Contract Research Organizations (CROs), this study aims to evaluate the safety and preliminary efficacy of hUC-MSC-sEV-001 in the treatment of ischemic stroke by enrolling a small sample population. Additionally, the study will explore and determine an appropriate dose to lay the foundation for subsequent research.

Research Methods

Clinical-grade hUC-MSC-sEV-001 produced under Good Manufacturing Practice (GMP) conditions will be obtained, and standardized procedures compliant with clinical research requirements will be established, covering aspects such as production, testing and identification, storage and resuscitation, transportation and packaging, and quality control.

Clinical research protocols, investigator's brochures, case report forms (CRFs), informed consent forms (ICFs), and recruitment advertisements will be developed, followed by submission for approval to the Ethics Committee (EC).

In accordance with the research protocol, 6–18 volunteers with ischemic stroke will be recruited to preliminarily explore the safety of hUC-MSC-sEV-001 in the treatment of cerebral ischemia. The optimal therapeutic and safe dose derived from animal experiments will be converted, and the corresponding treatment route and frequency will be determined. Safety assessments—including changes in vital signs and adverse reactions after treatment—will be conducted at baseline (Day 0–1), Day 7 (± 1), Day 14 (± 2), and Day 90 (± 7). Additionally, efficacy will be evaluated from the perspectives of laboratory indicators, imaging findings, neurological function assessment indicators, and follow-up data.

1. Study Design

(1) Overall Study Design

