- Confirmation of the MTD or identification of an unsafe dose level;
- Major flaws in the study design that affect data validity;
- Regulatory requirements (e.g., request by the National Medical Products Administration [NMPA]).

. Subject Withdrawal

Subjects may withdraw from the study at any time for the following reasons:

(1) Investigator-determined withdrawal:

① The subject develops a medical condition that makes continued participation unsafe (e.g., severe allergic reaction, intracranial hemorrhage);② The subject uses medications that interact with the study drug (e.g., immunosuppressants) or affect efficacy assessment (e.g., edaravone);③ The subject experiences a SAE that requires termination of study participation;④ The subject has poor compliance that compromises the reliability of safety or efficacy data.

(2) Subject-initiated withdrawal:

① The subject voluntarily requests to withdraw (no reason required);② The subject is lost to follow-up (no contact for ≥ 2 weeks).

For withdrawn subjects, the investigator shall conduct a final safety assessment (if possible) and document the reason for withdrawal in the CRF. Subjects who withdraw due to AEs/SAEs shall receive appropriate medical treatment, and follow-up shall continue until the AE/SAE resolves or stabilizes.

(7) Criteria for Terminating the Study

The study will be terminated immediately if any of the following occurs:

≥ 2 subjects experience DLT at the same dose level (indicating that the dose exceeds the MTD);

- Production of hUC-MSC-sEV-001 fails to meet quality standards for 3 consecutive batches, resulting in inability to administer scheduled doses;

- The study drug is found to have no clinical benefit (e.g., no improvement in neurological function in all enrolled subjects) or is associated with unexpected severe toxicity;
- A major protocol deviation is identified (e.g., incorrect randomization, unapproved dose modification) that invalidates the study results;
- The sponsor terminates the study due to funding, strategic adjustments, or other reasons;
- The Ethics Committee or NMPA issues an order to terminate the study.

3. Intervention Measures

(1) Trial Drug

- **Generic Name:** Human Umbilical Cord Mesenchymal Stromal Cell-Derived Small Extracellular Vesicle (hUC-MSC-sEV-001) Nasal Drops
- **Source:** Isolated and purified from the supernatant of hUC-MSCs cultured under GMP conditions

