 - Grade ≥ 3 laboratory abnormalities are summarized as frequency (percentage) by dose group.

(4) Sample Size Justification

This is a phase I dose-escalation study designed to explore the safety and MTD of hUC-MSC-sEV-001. Using the "3+3" design, a sample size of 6-18 subjects is sufficient to identify the MTD with a 90% probability of avoiding overdosing and a 80% probability of identifying the MTD if it exists.

(5) Statistical Software

All statistical analyses are performed using SAS 9.4 software (SAS Institute Inc., Cary, NC, USA). Two-sided tests are used, and a P-value < 0.05 is considered statistically significant.

(6) Interim Analysis

No interim analysis is planned for this study due to the small sample size. The study will be terminated early only if safety concerns arise (e.g., ≥ 2 subjects experience DLT at the same dose level).

12. Quality Control and Assurance

(1) Protocol Compliance

- **Training:** All study personnel (investigator, CRC, monitor, pharmacist) receive training on the study

protocol, GCP, and stem cell clinical research regulations before study initiation. Training records are retained in the study file.

- **Standard Operating Procedures (SOPs):** SOPs are developed for key processes, including subject screening, study drug administration, adverse event reporting, and data management. Study personnel strictly follow the SOPs to ensure consistency.
- **Protocol Deviation Monitoring:** The monitor records all protocol deviations (e.g., missed visits, incorrect dose administration) in the "Protocol Deviation Log". Major deviations are reported to the Ethics Committee and sponsor.

(2) Study Drug Quality Control

- **Manufacturing Quality:** The study drug is produced under GMP conditions, and each batch is tested for purity, potency, sterility, and endotoxin levels. A certificate of analysis (CoA) is provided for each batch.
- **Storage and Transportation:** Temperature monitoring during transportation and storage ensures that the study drug remains within the specified temperature range (-80°C ± 10°C). Temperature records are reviewed and archived.
- **Inventory Management:** The study drug inventory is checked monthly to ensure that the quantity administered matches the quantity received, and to prevent expiration or loss.

(3) Laboratory Quality Control

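### Section 1(2) names as MTD a dose with two or more DLTs; section 2(7) says the same count puts that dose above the MTD

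*Protocol*

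**What the plan says.** Section 1(2), Trial Administration Strategy, sets out the escalation rule. "If 1 out of 3 subjects experiences DLT, an additional 3 subjects are enrolled in the same dose group". No DLT among the added three allows escalation. If one or more of them has a DLT, "the current dose level is defined as the maximum tolerated dose (MTD), and dose escalation is terminated". This is the only place in the protocol that assigns the MTD to a dose level.

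Section 2(7), Criteria for Terminating the Study, orders immediate termination if "≥ 2 subjects experience DLT at the same dose level (indicating that the dose exceeds the MTD".

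Section 2(6)(i), Study Termination, gives as one reason for ending the study "Confirmation of the MTD or identification of an unsafe dose level", without a DLT count for either. Section 11(6), Interim Analysis, repeats the stop: "The study will be terminated early only if safety concerns arise (e.g., ≥ 2 subjects experience DLT at the same dose level". It does not mention the MTD.

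On purpose, section 11(4) describes a phase I study "designed to explore the safety and MTD of hUC-MSC-sEV-001". Under Main Research Content, "the study will explore and determine an appropriate dose to lay the foundation for subsequent research".

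**The concern.** Sections 1(2) and 2(7) give opposite verdicts on the same data. With one DLT in the first three subjects and at least one in the next three, section 1(2) makes the current dose the MTD, while section 2(7) places it above the MTD. With no order of precedence, the label could be settled after the data are known.

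The two rules also differ in consequence: section 1(2) ends escalation, section 2(7) ends the study. Both stop exposure to higher doses, so the safety of subjects in this trial is not at issue. At stake is the MTD that goes into the report and may guide later work.

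A smaller gap sits beside this. Section 1(2) does not say what the MTD is after two or more DLTs in the first three subjects (section 2(7) supplies the stop and the verdict), or when the top level passes.

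**Working it through.** **Step 1. Do the rules overlap? (No assumed rates needed.)** The inputs are the expansion and label rules in section 1(2) and the threshold in section 2(7). The protocol's maximum of 18 subjects is reproduced as 3 levels × 6, which confirms this reading of the expansion rule.

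The route to the MTD label is 1 DLT in the first three plus k in the next three, with k = 1, 2 or 3. The total at that level is 1 + k = 2, 3 or 4 among up to six. (Enrolment is one by one and section 2(7) acts immediately, so the second DLT may come before all six are enrolled.) Each total is at least 2, so every dose labelled MTD by section 1(2) exceeds the MTD by section 2(7). The overlap is complete.

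**Step 2. How likely is the branch at a level that is reached?** The protocol states no true or target DLT rate, so p is assumed. The 90% and 80% probabilities in section 11(4) cannot be checked for the same reason, and nothing here rests on them.

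- Escalate: e(p) = (1−p)³ + 3p(1−p)⁵
- Contradictory branch: f(p) = 3p(1−p)² × [1 − (1−p)³]
- At least 2 of the first 3: g(p) = 3p²(1−p) + p³
- Check: e + f + g = 1

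For p = 0.20: f = 3 × 0.20 × 0.64 × (1 − 0.512) = 0.384 × 0.488 = 0.187. Likewise f(0.10) = 0.066, f(0.30) = 0.290 and f(0.45) = 0.340.

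**Step 3. How often does the whole trial end there?** The probability is f₁ + e₁f₂ + e₁e₂f₃.

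For rates 5/20/45%: e₁ = 0.973, e₂ = 0.709, f₁ = 0.019, f₂ = 0.187, f₃ = 0.340. The terms are 0.019 + 0.182 + 0.235, which sum to 0.437 before rounding.

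| Assumed DLT rates, levels 1/2/3 | Trials ending in the contradictory label |
|---|---|
| 5/10/20% | 24.9% |
| 5/15/30% | 37.1% |
| 5/20/45% | 43.7% |
| 10/25/45% | 47.2% |

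**Step 4. What does a corrected label change?** When a level stops, the level below has already passed with 0/3 or 1/6. The corrected MTD is therefore exactly one level lower, or none if level 1 stopped.

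| Assumed rates | Level 3 to 2 | Level 2 to 1 | Level 1 to none |
|---|---|---|---|
| 5/20/45% | 23.5% | 18.2% | 1.9% |
| 10/25/45% | 18.5% | 22.1% | 6.6% |

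Under 5/20/45%, section 1(2) as written names the 45% dose as MTD in 23.5% of trials, against e₁e₂e₃ = 16.2% in which that dose actually passes. Under 10/25/45% the figures are 18.5% and 12.7%. Counting a passed top dose as the MTD in this comparison is an assumption; the protocol does not say so.

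Adjacent levels differ by a factor of five both in section 1(2) (2×10¹⁰, 1×10¹¹, 5×10¹¹) and in the synopsis (2.8×10¹⁰, 1.4×10¹¹, 7.0×10¹¹), so one level is a five-fold difference on either set.

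**Step 5. What do two DLTs in six show?** The exact (Clopper-Pearson) 95% interval for 2/6 is 4% to 78%. Such a result does not prove that the dose is too toxic. The fault is that the protocol gives it two incompatible names.

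**The case against.** The strongest reply concerns weight. No target DLT rate is stated, so the percentages count conflicting labels, not wrong doses. If a rate up to about 33% were acceptable, no dose in the 5/10/20% and 5/15/30% scenarios would be too toxic, and the correction would move the label down from an acceptable dose. Under 10/25/45%, 18.5% of trials would move off the 45% dose, but 22.1% + 6.6% = 28.7% would move off an acceptable one. This stands: the figures are frequencies of contradiction and should be read only that way. It does not rescue the rule, because section 2(7) has already decided that such a dose exceeds the MTD.

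Next, the MTD is not a listed endpoint, and section 13(2) requires DLT results in the final report but does not name the MTD. That is so, and a reader could work out the right answer from the counts. But section 11(4) makes the MTD a purpose of the study, and section 1(2) defines it.

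Three narrower points also have merit. Section 11(6) only restates the stop and agrees with both rules, so it needs alignment but is not part of the conflict. The item in section 2(6)(i) carries no counts; it shows only that the protocol treats a confirmed MTD and an unsafe dose as different outcomes. On a passed top level, section 11(4) already allows that an MTD may not exist, and how to report that could be left to an SAP.

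Finally, the corrected MTD may rest on 0/3, for which the exact 95% upper limit is about 71%. That is a real weakness of small cohorts and is taken up under the fix.

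**Conclusion.** The contradiction holds as written and needs no assumed rate: the protocol's only rule for assigning the MTD always picks a dose that section 2(7) places above the MTD. Nothing in the text reconciles the two.

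The effect is on the reported dose, by one five-fold step, or an MTD named where none was established if level 1 fails after expansion. It does not add exposure within the trial. Under the four assumed sets of DLT rates, 25% to 47% of trials would end with the contradictory label. How many of those labels would be truly too high depends on a target rate that the protocol does not give.

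This must be corrected, because a dose-finding trial cannot carry two opposite definitions of the dose it seeks.

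**What to change.** Replace the MTD clause in section 1(2) with:

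> At least 2 DLTs at a level (in the first 3 or among up to 6 subjects) means that the level exceeds the MTD, and escalation stops. The MTD is the highest lower level with no more than 1 DLT (0/3 or 1/6). If level 1 is stopped, no MTD is established. If level 3 passes, the MTD was not reached and level 3 is the highest tolerated dose tested.

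Use this one definition in sections 2(6), 2(7), 11(4) and 11(6). It agrees with section 2(7), follows the usual rule of the traditional 3+3 design the protocol adopts, and also closes the naming gap.

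The cost is one replaced clause and the matching references. Dosing and visits do not change. The reported MTD may be one level lower and may rest on three subjects. If the sponsor wants six at that level before naming it, section 2(7) needs an explicit exception to immediate termination so that the lower level can be expanded.
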